20. Recruitment Methods	18
21. Provisions to Protect the Privacy Interests of Subjects	19
22. Economic Burden to Subjects	19
23. Compensation	19
24. Compensation for Research-Related Injury	19
25. Consent Process	20
26. Documentation of Consent	21
27. Study Test Results/Incidental Findings	21
28. Sharing Study Progress or Results with Subjects	22
29. Inclusion of Vulnerable Populations	22
30. Community-Based Participatory Research	22
31. Research Involving American Indian/Native Populations	22
32. Transnational Research	22
33. Drugs or Devices	22
34. Principal Investigator's Assurance	23

1. Objectives

The primary objective of this research study is to perform a single-blinded, non-inferiority randomized-controlled trial to compare the effectiveness of two pre-surgical vaginal antiseptic cleaning solutions prior to pelvic surgery (which may include a vaginal approach or surgery on the vagina). Our central hypothesis is that chlorhexidine gluconate will be non-inferior to povidone iodine and that both antiseptic solutions will equally prevent postoperative infections. The specific aims are:

Aim 1: To compare postoperative urinary tract infection (UTI) rates between women cleaned with chlorhexidine gluconate (CHG) versus povidone iodine (PI) preoperatively. For the purposes of this study, UTI will be defined as: 1) greater than 100,000 CFUs on culture, or 2) at least 10,000 colony forming units on urine culture, in a symptomatic patient, or 3) patient reported UTI symptoms empirically treated within 2 weeks after surgery. Our primary **hypothesis** is that chlorhexidine gluconate will be non-inferior to povidone iodine with respect to the number of UTIs identified and treated within 2 weeks of surgery.

Aim 2: To compare postoperative culture proven urinary tract infection (UTI) rates between women cleaned with chlorhexidine gluconate (CHG) versus povidone iodine (PI) preoperatively. For the purposes of this aim UTI will be defined as: 1) greater than 100,000 CFUs on culture, or 2) at least 10,000 colony forming units on urine culture, in a symptomatic patient. Our primary **hypothesis** is that chlorhexidine gluconate will be non-inferior to povidone iodine with respect to the number of UTIs identified and treated within 2 weeks of surgery.

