Several studies demonstrate decreased SSI rates when chlorhexidine gluconate is used for abdominal preoperative antisepsis. Common abdominal surgeries such as hysterectomy and cesarean section demonstrate 44% and 19% lower odds when chlorhexidine gluconate is used instead of povidone iodine for preoperative surgical site antiseptic preparation. (Uppal et al) (Elshamy et al).

CHG is also known to have a longer duration of action than PI. While iodine has a duration of action of 2 hours, CHG has been characterized as having a duration of action of 6 to 48 hours depending on the level of alcohol concentration in the antiseptic solution. (Hemani et al)

Because of this, chlorhexidine is the preferred antiseptic of choice prior to abdominal surgeries.

For vaginal surgery, povidone iodine is the only FDA approved antiseptic agent. Because of this, some institutions limit or restrict the use of chlorhexidine vaginally. However, chlorhexidine has been shown to be a safe and effective vaginal presurgical antiseptic. (Al-Niaimi) The American College of Obstetricians and Gynecologists (ACOG) recommend that either CHG or PI are acceptable antiseptic agents. We are not aware of any studies directly comparing perioperative infection rates between CHG and PI at the time of pelvic surgery (which may include a vaginal approach or surgery on the vagina). A recent systematic review evaluating preoperative antisepsis at the time of vaginal hysterectomy identified minimal data, although one study which used bacterial colonies as a surrogate of SSI showed fewer bacteria sampled serially during a vaginal hysterectomy with CHG versus PI (Culligan). This corroborates the notion that CHG has a longer residual effect at the site of application over PI.

There have been no studies to specifically determine non-inferiority of chlorhexidine gluconate to povidone iodine for preoperative vaginal preparation prior to urogynecologic procedures with regard to either urinary tract infection or surgical site infection rates. Therefore, the primary objective of this study is to perform a single-blinded, non-inferiority randomized controlled trial to compare the effectiveness of two pre-surgical vaginal antiseptic cleaning solutions prior to pelvic surgery.

3. Study Design

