The primary outcome of this study is to determine rates of urinary tract infections in the period 2 weeks post-surgery for both cohorts. For the purposes of this study, UTI has been defined in section 1 (objectives), aim 1. We have powered the study based on a 10% difference in UTI rates between groups within 2 weeks of surgery. Based on a non-inferiority study design and a between group difference of less than or equal to 10%, we need 58 patients per group (chlorhexidine gluconate versus povidone iodine) to detect no difference with an alpha =0.05 and with 80% power. Assuming a high dropout rate of 20%, we will enroll a total of up to 200 patients (100/group), or until we reach our primary endpoint of 2 week follow up for 116 patients, or 58 patients in each group. We have increased the numbers due to COVID-19 and loss to follow-up.

This is not a multi-center study. Data will be housed at the Eubank clinic.

6. Study Timelines

Timeline	May 2019- April 2020	May 2020-Sept 2020
Subject recruitment, therapy, through 3 month follow up	x	x
Data analysis		x
Manuscript preparation		x

Over the past 12 months, 318 urogynecology cases were performed at UNM and SRMC. Assuming a conservative estimate of 50% enrollment, recruitment of up to 200 patients would be feasible over the next 3 month period.. Since subjects will be followed for 6 weeks after surgery, it may take up to 14 months to collect 6 weeks of follow up data. We estimate that data analysis, manuscript preparation and publication will take an additional 10 months.

7. Study Endpoints

The **primary endpoint** of our study is to determine the incidence of urinary tract infections within weeks of surgery in women who undergo pelvic surgery (which may include a vaginal approach or surgery on the vagina) with either chlorhexidine gluconate or povidone iodine vaginal antiseptic preparation. Our **secondary endpoints** are to investigate SSI rates in the two groups at 6 weeks, and vaginal irritation on the first postoperative day.

Given the extremely low-risk nature of the therapeutic interventions, we do not have any **safety endpoints**. However, any patients noted to have an allergic response will be treated according to the normal standard of care depending on the severity of their allergic reaction.

8. Research Setting

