 - c. an abscess or other evidence of infection involving the organ/space that is detected on gross anatomical or histopathologic exam, or imaging test evidence suggestive of infection. AND meets at least one criterion for a specific organ/space infection site.

13. Data Analysis

Data Analysis: Between and within group differences will be evaluated using Wilcoxon-Mann-Whitney test for categorical variables and t-tests for continuous variables. If there are any baseline differences between groups, a multivariate analysis will determine the contribution of these differences to observed differences (if any) between groups.

Power Analysis: Power analysis was performed based on previously reported rates of postoperative urinary tract infection after urogynecologic surgery as well as rates of relative reduction in infection with chlorhexidine presurgical preparations as opposed to povidone iodine. To achieve significance for a non-inferiority study using these assumptions we would need 116 patients, 58 per group to detect this difference with $\alpha = 0.05$ and with 80% power.

To allow for a dropout or loss to follow up of 20% due to the pandemic, we will enroll at least 200 patients.

Comparative Cost Analysis

The cost analysis will be conducted from patient and health system perspective and will be expressed as incremental cost required to prevent one episode of UTI.

Direct and indirect cost of health care utilization will be obtained when episodes of UTI occur, including the patient reported travel expenses and copays to obtain care, cost of UTI diagnosis with urine dipstick, urinalysis, and urine culture standardized to University of New Mexico Health Sciences Center institutional pricing as well as the cost of antibiotics for treatment.

14. Provisions to Monitor the Data to Ensure the Safety of Subjects

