There are no study related costs to the participant outside of what would be recommended for standard care. Whether enrolled in the chlorhexidine gluconate or povidone iodine, participants will not be billed outside of standard operating procedure for their surgical care.

23. Compensation

There will be no monetary compensation for involvement in the study.

24. Compensation for Research-Related Injury

If participants are injured or become sick as a result of this study, UNMHSC will provide emergency treatment at the study participant's cost. No commitment is made by the University of New Mexico Health Sciences Center to provide free medical care or money for injuries to

participants of the study. Reimbursement for treatment for all related costs of care will be sought from the participant insurer, managed care plan, or other benefits program. The participant will be responsible for any associated co-payments or deductibles required by the insurance. Participants will be encouraged to report any illness or injury they believe to be related to the study to the investigator or research staff. Participants will be given telephone contact information for the urogynecology office for the purpose of asking any questions or stating any concerns about the study or treatment as a research subject. They may also be directed toward the HRPO. This language will be stated in the written consent document, and reviewed during the informed consent process

25. Consent Process

Patients will be approached about the research study at the urogynecology clinic at UNM Eubank and at SRMC or the associated hospitals at UNM Hospital or SRMC Hospital during a discussion for the management of their urogynecologic condition. Each patient undergoes counseling in a private room with a closed door to ensure privacy. The physicians in the urogynecology division and research staff will be able to obtain consent after the participants have been counseled about their condition. Our division routinely treats this condition and are highly qualified to counsel patient regarding the risks, benefits, alternatives for the treatment. Those recruited will have already decided to undergo surgical management for their urogynecologic conditions. Hence, they will not be coerced into performance of any “extra” treatments. Additionally, care will not be withheld if they decide not to participate.

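### If only the named UTI-triggered costs are used, the planned cost per UTI prevented centres on minus the cost of one UTI whichever preparation does better, so by itself it cannot show which is cheaper

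*Combined protocol and SAP*

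**What the plan says.** Section 13 (Comparative Cost Analysis) sets two viewpoints: "The cost analysis will be conducted from patient and health system perspective". The result "will be expressed as incremental cost required to prevent one episode of UTI". No other cost summary, interval or rule for reading a negative value is given in that paragraph.

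On inputs it says: "Direct and indirect cost of health care utilization will be obtained when episodes of UTI occur". The items listed are patient travel and copays, dipstick, urinalysis and culture at institutional prices, and antibiotics. Each belongs to a UTI episode. The list is worded as open, so the preparation price is not ruled out, but it is not named.

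Four other places bear on the point:
- Section 1 (Objectives) gives the central hypothesis of non-inferiority and that "both antiseptic solutions will equally prevent postoperative infections".
- Section 5 (Number of Subjects) allows enrolment to run "or until we reach our primary endpoint of 2 week follow up for 116 patients, or 58 patients in each group".
- Section 22 (Economic Burden to Subjects) says "participants will not be billed outside of standard operating procedure for their surgical care".
- Sections 1 and 7 do not list cost among the aims or endpoints.

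**The concern.** A cost-effectiveness ratio informs a choice when one option costs more and does more. Here, if the costs counted are those of UTIs, the numerator is the UTI difference multiplied by the cost of a UTI, and the denominator is the same difference with its sign reversed. The difference cancels, and what remains is the cost of one UTI with a minus sign. A preparation that prevents infections and one that causes them would then yield about the same figure.

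The second difficulty does not depend on which costs are counted. The plan expects the two rates to be about equal, so the denominator is expected to be near zero. A ratio with such a denominator swings widely and has no value when the rates tie.

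At stake is the cost statement for each perspective. The primary UTI comparison is not touched.

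**Working it through.** The documents give no cost figure, so there is none to reproduce.

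**Inputs**
- Form of result and costs counted: section 13.
- 58 women per arm: section 5.
- Size of a possible effect: section 2 (Background) reports that abdominal operations "demonstrate 44% and 19% lower odds when chlorhexidine gluconate is used instead of povidone iodine". These figures are borrowed, since they concern abdominal preparation.
- Assumed, because not given: mean cost per UTI c = $200 (SD $100, gamma), the same in both arms; a 20% UTI rate in the worse arm; equal true rates of 5% to 33% for the stability check; preparation price difference D (chlorhexidine, CHG, minus povidone iodine, PI), tried from $0 to $20. With D = 0, all results scale with c.

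**Step 1: named costs only**

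Ratio = (c·p_CHG − c·p_PI) / (p_PI − p_CHG) = −c for any unequal rates.

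In counts at 58 per arm, with every UTI costing $200:
- 3 UTIs with CHG, 6 with PI: (600 − 1,200)/58 ÷ (6 − 3)/58 = −600/3 = −$200.
- 9 with CHG, 2 with PI: (1,800 − 400)/58 ÷ (2 − 9)/58 = 1,400/(−7) = −$200.

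**Step 2: mirror-image truths with random episode costs**

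44% lower odds from 20%: odds 0.25 × 0.56 = 0.14, and 0.14/1.14 = 12.3%. Simulation of 400,000 trials, 58 per arm, D = 0:

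| True rates | Ratio, median (95% range) | Mean cost difference per woman (95% range) |
|---|---|---|
| CHG 12.3%, PI 20% | −$199 (−$583 to +$183) | −$15 (−$46 to +$15) |
| CHG 20%, PI 12.3% | −$199 (−$584 to +$182) | +$15 (−$15 to +$46) |

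The ratio does not register the reversal; the mean difference changes sign. With 19% lower odds (16.8% against 20%) the median ratio is still −$199 and the mean difference is about −$6.

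**Step 3: unequal cost per UTI**

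If a UTI costs 20% more in the CHG arm:
- CHG 5%, PI 10%: (1.2 × 0.05 − 0.10)c/0.05 = −0.8c.
- CHG 10%, PI 5%: (1.2 × 0.10 − 0.05)c/(−0.05) = −1.4c.

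The value moves, but it is negative both ways.

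**Step 4: preparation price added**

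Ratio = −c + D/(p_PI − p_CHG). With D = 0.01c:
- CHG 5%, PI 10%: cost difference −0.05c + 0.01c = −0.04c, ratio −0.04c/0.05 = −0.8c. CHG is cheaper.
- CHG 10%, PI 5%: cost difference +0.05c + 0.01c = +0.06c, ratio 0.06c/(−0.05) = −1.2c. PI is cheaper.

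Both ratios are negative, yet they point to different arms. In the simulation of step 2 the two medians now separate: −$154 against −$244 at D = $5, and −$4 against about −$396 at D = $20. The 95% ranges still overlap widely.

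**Step 5: stability at equal true rates, 58 per arm**
- D = 0: 95% range from −$557 to +$148 at a 5% rate, up to −$879 to +$476 at 33%. The rates tie exactly, leaving the ratio undefined, in 8% to 17% of trials.
- 10% rate: −$795 to +$391 at D = $5; −$1,648 to +$1,252 at D = $20. The mean cost difference stays centred on D, with a 95% range of about ±$25 per woman.

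The ratio is in dollars per UTI and the difference in dollars per woman, so their widths should not be compared. The point is that the second is centred on the quantity of interest and is always defined.

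**The case against.** The strongest objection is that the cost required to prevent a UTI would naturally include the price of the preventive agent, and that the itemised sentence merely describes how episode costs are gathered. This stands. A reader might infer that the plan leaves the preparation price out, and hence that its ratio must be uninformative. The documents do not support that: the list is open and the price is not excluded. The −c result therefore holds only if the named costs are all that is used. Step 4 shows that a price difference restores some information, without curing the instability or making the sign readable.

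A reader might also infer that nothing but the ratio would be seen. In fact the UTI rates by arm are the primary outcome, and anyone who has them can work out the direction. Section 13 also plans t-tests for continuous variables generally, without naming any variable. So the criticism is of the ratio taken alone.

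Third, on the named costs the mean cost difference is the UTI difference rescaled in dollars. That is true. It adds a readable sign and an interval rather than much new information, which is why naming the preparation price matters as well.

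Finally, section 22 might be read as showing that the preparation price never reaches the patient. It rules out billing beyond standard procedure; it does not say how the preparation itself is charged.

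**Conclusion.** The point holds conditionally. If only the named costs are used and the mean cost per UTI is the same in both arms, the ratio centres on minus the cost of one UTI whichever preparation does better, and alone it cannot show which is cheaper. The algebra needs no dollar figure. The equal-cost assumption is reasonable, since tests are priced from one institutional list, and a 20% departure leaves the ratio negative in both directions in the case tried.

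If a preparation price difference is included, the ratio becomes informative but remains unstable under the plan's own expectation of equal infection, and its sign still does not identify the cheaper arm.

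The dollar magnitudes rest on the assumed $200 per UTI, the assumed rates and the assumed price differences. Priority is low: cost is neither an aim nor an endpoint, and nothing here affects the non-inferiority conclusion.

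**What to change.** Revise the cost paragraph of section 13 as follows.

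- **Main result.** For each perspective, report the between-arm difference in mean cost per woman with a 95% interval (for example, bootstrap), beside the UTI rate difference with its interval, in the same analysis set as the primary UTI outcome.
- **Preparation price.** Name the unit price of the assigned preparation as an input to the health-system perspective. Include it in the patient perspective only if it is actually charged to the patient.
- **Women without a UTI.** For those followed, count any UTI-related work-up cost incurred, such as tests that proved negative, and otherwise zero.
- **Women lost to follow-up.** Do not assign them zero cost. The plan enrols extra women "To allow for a dropout or loss to follow up of 20% due to the pandemic", so this matters. For example, with $200 per UTI, equal 20% rates and assumed losses of 15% and 25%, zero-filling creates a false difference of 200 × (0.20 × 0.85 − 0.20 × 0.75) = $4 per woman.
- **Ratio.** Keep it as supplementary, with uncertainty shown by a method that tolerates a near-zero denominator (cost-effect plane, net benefit or Fieller), and state that it is not reported if the rates are equal.

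The cost is a few lines of text, slightly more analysis and two unit prices, assumed obtainable from the institution. Work-up costs in women without a UTI should be recorded where they occur. A percentile bootstrap interval is a little short when UTIs are few (92% to 93% coverage at a 5% rate in simulation), which is acceptable for a result of this standing.

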We will perform a single masked, non-inferiority randomized-controlled trial to compare the effectiveness of chlorhexidine gluconate and povidone iodine pre-surgical vaginal antiseptic cleaning preparations prior to pelvic surgery (which may include a vaginal approach or surgery on the vagina). The target population are those patients presenting for urogynecologic surgery in the University of New Mexico health system. Participants will be masked as they will not be informed regarding which intervention they receive while under anesthesia at the start of their scheduled procedure. All women will give written or verbal consent prior to enrollment. It is not feasible to mask the surgeon, as the two antiseptic preparations are colored differently which is evident throughout surgery.

4. Inclusion and Exclusion Criteria

We will recruit patients who present to the University of New Mexico (UNM Women's Care Eubank Clinic or Sandoval Regional Medical Center) with urogynecologic conditions requiring pelvic surgery (which may include a vaginal approach or surgery on the vagina). Patients will receive usual care including evaluation of prior medical history and physical exam, any necessary diagnostic studies and preoperative workup. All patients will be offered typical treatment options regardless of their desire to participate in the research study.

Patients will be enrolled if they meet the inclusion and do not meet the exclusion criteria.

The inclusion criteria are:

- Female Subjects >18 years of age
- English or Spanish speaking/reading
- Must be able to provide informed consent.
- Undergoing urogynecologic procedures or surgery at UNM, OSIS, or SRMC

Exclusion criteria:

- Pregnant - all patients are verified regarding pregnancy status prior to gynecologic surgical intervention at all sites of surgery within the UNM system –

for patients who are premenopausal and have a uterus, a urine pregnancy test is administered in the preoperative setting. Pregnancy status is also determined prior to this in the office setting by interview and patient provided history prior to offering surgery to the patient.

- Inability to return for follow-up visits
- No concurrent need for vaginal antiseptics, such as cases of sacral neuromodulation
- Lack of telephone
- Known allergy to either antiseptic agent
- Prisoners will not be eligible to participate in this study

5. Number of Subjects

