The study will be performed at the University of New Mexico Hospital (UNMH), Sandoval Regional Medical Center (SRMC) and University of New Mexico Outpatient Surgery and Imaging Services OSIS, and all associated urogynecology clinics. Potential subjects will be recruited in the UNM Eubank and SRMC clinics. All patients will have a complete history and physical taken. They will undergo a pelvic exam and will undergo typical preoperative diagnosis and workup performed as part of the standard of care for their respective urogynecologic diagnosis. After recruitment, they will undergo the consent process, and fill out initial questionnaires in the outpatient offices or by phone. All other follow-up will be performed in the above-mentioned outpatient clinics.

There are no laboratory tests in this trial other than what would routinely be collected for the workup of urogynecologic conditions or postoperative infections or complications. As we are essentially comparing two standard treatment options we do not think community advisory board is necessary. There will not be any research conducted outside of the UNM HSC and its affiliates.

9. Resources Available

[name] is a board certified subspecialist in Urogynecology and will serve as the primary investigator (PI) for this study. In addition, Drs. [name] and [name] will also help oversee and mentor [name] with this study; they are both very experienced researchers. All have been PIs on multiple research trials and has successfully completed and published many studies. [name] is a Female pelvic medicine and reconstructive surgery (urogynecology) fellow. He has the time and resources including 12 months of protected research time, to complete this study.

The University of New Mexico (UNM) urogynecology division evaluates patients primarily in two outpatient clinics. UNM Eubank Urogynecology Clinic located in Northeast Albuquerque provides a full range of services for women with pelvic floor disorders. The Eubank clinic consists of 8 examination rooms, 2 treatment rooms, and 2 physical therapy rooms. Our second location is at Sandoval Regional Medical Center (SRMC), a community-based facility located in Rio Rancho, New Mexico, a large suburb located north of Albuquerque.

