Research Staff: The Urogynecology Division employs a clinical research manager, 3 research coordinators and one student research assistant. Our research staff has extensive experience conducting multi-center investigations and recruiting patients to clinical studies, with special expertise in community-based research and quality of life studies.

Research Experience: The Urogynecology Division at UNM has a strong history of conducting high quality research and collaboration with other investigators in the US and abroad, and has consistently met or exceeded recruitment goals on time. We have been members of the NICHD-sponsored Pelvic Floor Disorders Network, and have met recruitment goals with high rates of follow-up and accurate data collection. In addition to PFDN research, [name] has mentored and has been the PI on multiple clinical trials and contributes multiple publications in peer-reviewed journals. His Curriculum Vitae is attached.

Our group is well versed in the importance of adherence to protocols, timely completion of regulatory requirements, effective recruitment strategies, and the importance of the inclusion of minority subjects. Research is integral to all aspects of Divisional work; importantly, all members of the clinical team participate in research efforts. There are weekly research meetings to discuss the progress of the ongoing studies within the department, and it is an excellent forum to ensure that all involved are adequately informed of their duties, of the protocol, and of the procedures.

We do not anticipate that emergency care outside of normal operating protocol will be needed for this study; however the urogynecology physicians are available on a 24 hour basis, 7 days per week for any patients requiring emergency care.

10. Prior Approvals

This is a new study that has not been previously submitted for approval but Institutional Review Board approval for the University of New Mexico Health Sciences Center will be obtained prior to initiating the study.

This study has been approved by the Department Scientific Review Process for the Obstetrics and Gynecology Department by [name].

This study does not include any ionizing radiation, or biological specimens. The drugs that are used in this study include Povidone Iodine and Chlorhexidine Gluconate.

11. Multi-Site Research

This is not a multi-site research study.

12. Study Procedures

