Randomization assignment will be generated by a computer based randomization table and assigned by a research coordinator. Assignments will be kept in sealed opaque envelopes numbered sequentially, and on the day of the patient's surgery a research coordinator will open the next envelope in the sequence. This de-identified study subject number will then be assigned to the patient. All data collection sheets and questionnaires will contain the subject number and day of the enrollment. No other patient identifiers will be collected on study forms. PHI including patient name, date of birth, phone number, and medical record number will be collected to track appointments and kept separate from participant study data in a locked cabinet in a locked secured office.

The data collection, HIPAA and consent forms will be maintained in a locked file cabinet in the locked Eubank research office. A separate folder will be designated for each participant. The offices have the additional security of being badge-access only for UNM OBGYN department employees. A key matching study number to subject's name will be stored on a password protected computer on a secure UNM OBGYN department server.

The only identifiers collected will be patient name, date of birth, and telephone number for site use only and to ensure patient follow up. This will not be entered into the database, but it will be kept with the other identifying information.

The data does not include sensitive information or information requiring additional protection.

All data will be kept in a locked file cabinet in the research administrative area. In order to further ensure patient confidentiality, the identifying information will be kept separately from the numbered study files in a locked cabinet.

Electronic data entry will be performed in the OBGYN administrative offices, using the de-identified subject study number. The electronic data will be encrypted, password protected, and stored on the secure UNM OBGYN department server. This server's electronic security is

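### The surgeon and the coordinator who opens the envelope know the arm, the primary UTI outcome is partly discretionary, and no masked interviewer or outcome classifier is planned

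*Combined protocol and SAP*

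**What the plan says.** **Masking.** The design is single-masked. Section 3 states: "Participants will be masked as they will not be informed regarding which intervention they receive". It continues: "It is not feasible to mask the surgeon, as the two antiseptic preparations are colored differently which is evident throughout surgery". That gives a reason for the surgeon. It says nothing about whoever interviews the woman or classifies her outcome.

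**Allocation.** Section 16 states: "Randomization assignment will be generated by a computer based randomization table and assigned by a research coordinator". On the day of surgery, "a research coordinator will open the next envelope in the sequence".

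**Primary outcome.** Aim 1 in Section 1 has three routes to a UTI: a culture above 100,000 CFU, a culture of at least 10,000 CFU with symptoms, or "patient reported UTI symptoms empirically treated within 2 weeks after surgery". The outcome list in Section 12 makes clear that the third route needs no culture. Aim 2 repeats the comparison without that route.

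**Case finding.** Section 8 states: "There are no laboratory tests in this trial other than what would routinely be collected". Follow-up at 2 and 6 weeks is in the division's own clinics, with telephone contact as a fallback (Sections 8 and 12). The caller is not identified.

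**Staff.** Section 9 says the division "employs a clinical research manager, 3 research coordinators and one student research assistant".

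**The concern.** Whether a woman counts as a UTI depends on choices made after surgery: whether urine is sent, whether symptoms are treated without a culture, and how symptoms are asked about and recorded. A positive culture without symptoms counts, but it exists only if someone decided to culture. At least two people know the arm, the surgeon and the coordinator who opened the envelope. The plan does not exclude either of them from these steps.

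In a non-inferiority comparison, events missed in the chlorhexidine (CHG) arm pull the observed difference towards a favourable conclusion. Events missed in the povidone iodine (PI) arm push it the other way and can hide true non-inferiority. With groups this small, a handful of women is enough to matter.

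**Working it through.** **Inputs from the documents (Section 5).** 58 evaluable women per group, a margin of 10 percentage points, alpha 0.05 with sidedness not stated, and 80% power.

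**Assumptions, because the documents do not give these.** PI rates of 5% and 20%; a Farrington-Manning test (Section 13 names no non-inferiority test); one-sided 0.05; and 10-30% of the UTIs in one arm uncounted.

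**The plan's own figure.** Section 5 states no UTI rate, so 58 cannot be confirmed. With an assumed 5% in both arms and one-sided 0.05:

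n = (1.645 + 0.842)² × 2 × 0.05 × 0.95 / 0.10² = 58.7, so 59 per group.

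At 33%, the only UTI rate quoted (12 weeks after stress incontinence surgery, Section 2), the same formula gives 274. The present point does not depend on which rate was used.

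**Weight of one woman.** 1/58 = 1.7 points. The whole margin is 0.10 × 58 = 5.8 women.

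**Apparent difference when CHG is truly 10 points worse and 30% of one arm's UTIs are missed:**
- 15% vs 5%, missed in CHG: 0.7 × 15 − 5 = 5.5 points. This is 0.3 × 0.15 × 58 = 2.6 women.
- 30% vs 20%, missed in CHG: 0.7 × 30 − 20 = 1 point. This is 0.3 × 0.30 × 58 = 5.2 women.
- Missed in PI instead: 15 − 0.7 × 5 = 11.5 points, or 30 − 0.7 × 20 = 16 points.

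**Chance of declaring non-inferiority.** The statistic is Z = (observed CHG rate − observed PI rate − 0.10) / SE. The SE uses the maximum-likelihood rates constrained to differ by 0.10, with 58 per arm. Non-inferiority is declared if Z ≤ −1.645. The probability is the sum, over all 59 × 59 pairs of counts, of the product of the two binomial probabilities wherever the rule is met. The rate in the affected arm is multiplied by 0.9, 0.8 or 0.7.

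| True CHG vs PI | Equal counting | 10% of CHG UTIs missed | 20% | 30% | 10% to 30% of PI UTIs missed instead |
|---|---|---|---|---|---|
| 15% vs 5% | 4.5% | 7.6% | 12.4% | 19.5% | 3.7% to 2.3% |
| 30% vs 20% | 5.2% | 10.7% | 19.8% | 33.1% | 3.0% to 0.8% |

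At one-sided 0.025 with 10-30% of CHG UTIs missed, the figures are 2.3% rising to 4.1-12.0%, and 2.6% rising to 6.0-22.5%.

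**The case against.** **Participants are masked, and Aim 2 drops the empiric route.** Both are true and both help. The women report the symptoms, and Aim 2 removes the most discretionary route. But Aim 2 is not the primary outcome, and it still depends on who was cultured.

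**The UTI rule is close to mechanical once symptoms, culture count and antibiotic date are recorded.** This largely stands. Masking the person who applies the rule removes only part of the discretion. The larger part lies in the decision to send urine or to treat, which belongs to clinicians who may know the arm. Masked interviewing standardises how symptoms are elicited, but it cannot recover a culture that was never sent.

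**Stronger readings that the documents do not support:**
- A reader might infer that coordinators who know the arm decide who is cultured, treated or coded as a UTI. No section says so. Section 16 shows only that a coordinator assigns and opens the envelope. The gap is that nothing rules the overlap out.
- A reader might infer that masked follow-up would cost nothing because three coordinators are listed. Section 9 lists the division's staff, not staff assigned to this trial. No workload or staffing cost is given, surgery takes place at three facilities (Section 8), and Section 25 has coordinators mainly working from home.
- A reader might take the table as a forecast, or as the gain from the fix. It is neither, because nothing in the documents indicates the size or direction of differential counting.

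**Conclusion.** The point holds as a design improvement. The surgeon and at least one coordinator know the allocation, part of the primary outcome is discretionary, culturing is not standardised, and no masked interviewer or classifier is planned. The sensitivity is real: each woman is worth 1.7 of the 10 points. Under the assumed rates, one-sided test and 10-30% loss, false non-inferiority could reach 19.5% or 33.1% if the loss falls on the CHG arm, or drop to 2.3% or 0.8% if it falls on the PI arm. These figures show how much equal counting matters. They are not evidence that counting will be unequal. The change is worth making, but its absence does not by itself invalidate the trial.

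**What to change.** In Sections 12 and 16, state that:

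1. The coordinator who opens a woman's envelope does not conduct her 2- and 6-week research contacts and does not code her outcome.
2. Another existing coordinator, without access to the allocation, asks the standard follow-up questions and applies the UTI rule to records that do not show the arm. Section 16 appears to tie the subject number to the envelope sequence, so the randomization table must also be kept from this person.
3. The report gives, by arm, the number of women cultured and the number treated without culture, so that unequal case finding can be seen.

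The cost is some task scheduling among the existing coordinators, assuming workload allows, plus two extra counts per arm in the report. No added test and no change to the sample size or to clinical care is needed. Clinicians' decisions to culture or treat remain unmasked. The report should state that as a limitation.
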